10.4.2. Serious Adverse Events

All SAEs, regardless of assessment of causal relationship to study drug, must be reported to the sponsor (or designee) within 24 hours. Refer to the study reference manual for the procedure to be followed.

Information not available at the time of the initial report must be documented in a follow-up report. Substantiating data such as relevant hospital or medical records and diagnostic test reports may also be requested. In the event the investigator is informed of an SAE after the subject completes the study (ie, the follow-up period), the following will apply:

- If the subject is an early termination from the study, SAE with an onset within 12 weeks of last study drug administration will be reported to the sponsor. The investigator should make every effort to obtain follow-up information on the outcome until the event is considered chronic and/or stable.
- For SAEs with an onset day greater than 12 weeks from the last study drug administration, only those deemed by the investigator to be drug-related SAEs will be reported to the sponsor. The investigator should make every effort to obtain follow-up information on the outcome of a drug-related SAE until the event is considered chronic and/or stable.

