3.3. The Safety Analysis Set (SAF)

SAF includes all randomized subjects who receive at least one injection of dupilumab/placebo and be analyzed as treated. Treatment assignment will be based on the actual treatment received not the treatment assigned by IWRS randomization. Treatment compliance/administration for investigational product including both dupilumab/placebo and AR101, as well as all clinical safety variables will be summarized based on SAF.

For the safety analyses during the maintenance period, a subset of SAF which is defined as SAF-maintenance includes re-randomized subjects at visit 16 who received at least one injection of dupilumab/placebo during the maintenance period. Treatment compliance/administration for investigational product and all clinical safety variables during maintenance period will be summarized based on SAF-maintenance.

The actual treatment group as treated is defined by the following rule:

- For a subject randomized to dupilumab Q2W (any dose level), if the subject received all placebo injections, the actual treatment will be assigned as placebo.
- Regardless of the treatment group a subject is randomized to, if the subject received at least 1 dupilumab injection, the actual treatment will be assigned as dupilumab Q2W (any dose level).

For safety summaries, the analysis periods are defined as follows:

- Pre-dosing period (4 weeks) is defined as:
 - Day 1 to the day before the date of AR101 IDED in the up-dosing period if subjects completed the IDED at Week 4
 - Day 1 to early termination (ET) visit date before Week 4 if subjects early terminated from the pre-dosing period
- Up-dosing period (24 to 36 weeks) is defined as:
 - For subjects who entered maintenance period: The date of AR101 IDED to the date of second post up-dosing DBPCFC at visit 16.
 - For subjects who did not enter maintenance period:
 - The date of AR101 IDED at Week 4 to the date of visit 16 if subjects entered follow-up period
 - The date of AR101 IDED at Week 4 to the last dose date of dupilumab/placebo + 14 days if subjects completed dosing to visit 16 but did not enter follow-up period
 - The date of AR101 IDED at Week 4 to early termination (ET) visit date before visit 16 if subjects did not complete dosing to visit 16
- Maintenance period (24 weeks) for subjects who entered maintenance period is defined as:

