 - The day after the date of second post up-dosing DBPCFC at visit 16 to the date of second post maintenance DBPCFC at visit 22 if subjects completed the visit 22 with known visit date
 - The day after the date of second post up-dosing DBPCFC at visit 16 to study day 365 (52 weeks times 7 days/week + 1 day) if subjects had missing visit 22 date
 - The day after the date of second post up-dosing DBPCFC at visit 16 to ET visit date before visit 22 if subjects early terminated from maintenance period
- Follow-up period (12 weeks) for subjects who entered follow-up period is defined as:
 - For subjects who completed maintenance period: The day after the date of second post maintenance DBPCFC at visit 22 to the subject end of study visit date or the date of second end of study DBPCFC at visit 25, whichever comes later

- For subjects who did not receive 300 mg/day of AR101 for at least two weeks by visit 16 : The day after the visit 16 date to the subject end of study visit date
- For subjects who early terminated from study treatment in the up-dosing period or maintenance period: The day after the last visit date in the treatment period to the subject end of study visit date
- Overall study period is defined as Day 1 to the date of end of study visit.

The SAF and SAF-maintenance will be the basis for the analyses of the pre-dosing/up-dosing period and maintenance period, respectively; however, for the analyses of the follow-up period, only a subset of the corresponding safety analysis sets will be included, which is defined as the subjects who entered the follow-up period from pre-dosing/up-dosing period and had at least one visit after visit 16 (for SAF) or subjects who entered the follow-up period and had at least one visit after visit after visit 22 (for SAF-maintenance).

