5.7.1. Adverse Events

The number and proportion of subjects reporting TEAEs will be summarized for pre-dosing period, up-dosing period, maintenance period and follow-up period separately, as described in Section 3.3.

AE incidence tables will be presented by treatment group for the SAF and SAF-maintenance as well as subgroups. Summary of TEAEs will present the number (n) and percentage (%) of subjects experiencing an TEAE by SOC, and PT, sorted by decreasing frequency of SOC and PT for the dupilumab treatment group in the pre-dosing period, dupilumab plus AR101 treatment group in the up-dosing period, and continuously on dupilumab plus AR101 treatment group in the maintenance period. Multiple occurrences of AEs of the same PT (or SOC) in the same subject will be counted only once for that PT (or SOC). For AE tables presenting severity, the worst severity will be chosen for subjects with multiple instances of the same event. The denominator for computation of percentage is the number of subjects in each treatment group for the corresponding analysis period as specified in Section 3.3.

An overall summary of TEAEs will be provided with number and proportions of subjects with any:

- TEAE
- Serious TEAE
- TEAE of special interest (AESI)

- TEAE/Serious TEAE leading to death
- TEAE/Serious TEAE leading to permanent treatment discontinuation
- TEAE/Serious TEAE of injection site reaction
- Study drug related TEAE/serious TEAE

Detailed summaries of TEAEs will include:

- TEAEs
 - TEAEs by SOC/PT
 - TEAEs by SOC/HLT/PT
 - TEAEs by PT
 - TEAEs by SOC/PT with incidence of $PT \ge 5\%$ in any treatment group
 - TEAEs by severity and by SOC/PT
 - Severe TEAEs by SOC/PT
 - TEAEs related to dupilumab/placebo as assessed by the investigator by SOC/PT
 - TEAEs related to AR101 as assessed by the investigator by SOC/PT
 - Severe TEAEs related to dupilumab/placebo as assessed by the investigator by SOC/PT
 - Severe TEAEs related to AR101 as assessed by the investigator by SOC/PT
 - TEAE of special interest
- Serious TEAEs:
 - Serious TEAEs by SOC/PT
 - Serious TEAEs related to dupilumab/placebo as assessed by the investigator by SOC/PT
 - Serious TEAEs related to AR101 as assessed by the investigator by SOC/PT
- TEAEs leading to permanent discontinuation of study treatment by SOC/PT
- Death by SOC/PT

Number and proportion of subjects reporting pre-treatment adverse events will be tabulated by SOC and PT.

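### SAEs after the final visit, in subjects who leave without a follow-up visit, fall in no SAP safety period, and the follow-up tables exclude anyone who dies before returning

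*SAP*

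**What the plan says.** **Reporting.** Protocol section 10.4.2 covers SAEs that come to the investigator's notice after a subject has completed the study. "If the subject is an early termination from the study", it says, an "SAE with an onset within 12 weeks of last study drug administration will be reported to the sponsor". Protocol section 6.1 gives the reason for a 12-week follow-up: the time drug levels are expected to need to fall below quantification.

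**Analysis periods.** SAP section 3.3 closes the periods as follows:
- Pre-dosing: "Day 1 to early termination (ET) visit date before Week 4 if subjects early terminated from the pre-dosing period".
- Up-dosing, dosing not completed: the period runs "to early termination (ET) visit date before visit 16 if subjects did not complete dosing to visit 16".
- Up-dosing, dosing completed to visit 16 but no follow-up: last injection + 14 days.
- Maintenance, terminated early: the ET visit.
- Follow-up, for those who stopped treatment early in up-dosing or maintenance: "The day after the last visit date in the treatment period to the subject end of study visit date".
- Overall study period: day 1 to the end-of-study visit.

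**Membership of follow-up tables.** For the SAF, only subjects who "entered the follow-up period from pre-dosing/up-dosing period and had at least one visit after visit 16 (for SAF") are included. SAF-maintenance has the matching condition at visit 22.

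**Use.** SAP section 5.7.1 states: "The number and proportion of subjects reporting TEAEs will be summarized for pre-dosing period, up-dosing period, maintenance period and follow-up period separately". Its denominators come from section 3.3.

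**The concern.** The reporting rule and the analysis periods stop at different dates. The protocol treats the 12 weeks after the last dose as a time when an SAE still matters. The SAP closes a departing subject's last period at the final visit or at two weeks after the last dose. An SAE reported in between has no period to be counted in, and TEAEs are tabulated by period.

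The membership rule is a separate fault. Being counted in the follow-up tables requires attending again. A subject who dies or is incapacitated after the treatment period closes, but before the first follow-up visit, leaves both numerator and denominator. The table is thus conditioned on the outcome it reports. This can also touch subjects who completed treatment.

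Those who leave early are not a random sample. Protocol section 6.1.1.1 has subjects who do not tolerate the initial escalation day because of moderate or severe reactions terminated from the study. Tolerability is an objective, so exit could differ by arm.

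**Working it through.** The plan states no figure for this gap, so there is none to reproduce. The check is interval arithmetic on the two documents' own dates.

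**Inputs**
- Reporting window: 12 weeks = 12 × 7 = 84 days from last study drug (protocol 10.4.2), read here as the last dupilumab or placebo injection.
- Period end for dosing completed without follow-up: last injection + 14 days (SAP 3.3).
- Period end for leaving at an ET visit: the date of that visit (SAP 3.3). The interval *d* from last dose to ET visit is not stated, so a range is shown.
- Randomized: 156, as 104 + 52 (SAP 2.1).
- Discontinuation, for scale only: 20.4% of AR101-treated subjects in the phase 3 AR101 study (protocol 3.2.1).

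**Uncovered days** = 84 − (days from last dose to the end of the subject's last period)

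| Subject | Days covered after last dose | Uncovered days |
|---|---|---|
| Completed dosing to visit 16, no follow-up | 14 | 84 − 14 = 70 (83%) |
| Leaves at ET visit, *d* = 0 (assumed) | 0 | 84 |
| Leaves at ET visit, *d* = 14 (assumed) | 14 | 70 |
| Leaves at ET visit, *d* = 28 (assumed) | 28 | 56 |
| Leaves at ET visit, *d* = 42 (assumed) | 42 | 42 |
| Leaves at ET visit, *d* = 84 (assumed) | 84 | 0 |
| Stops treatment, attends follow-up to about 12 weeks | about 84 | about 0 |

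For someone who leaves at the ET visit, the follow-up period does not help. It starts the day after the last treatment-period visit and ends at the end-of-study visit. With no later visit, it has no length.

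**Later-visit condition.** Visit 22 is 24 weeks after visit 16 and visit 23 is 28 weeks after it, so the first follow-up visit is nominally 4 weeks after maintenance ends. SAP 6.4 likewise puts visit 23 at 28 days after the last treatment-period visit. A death in those 4 weeks removes the subject from the follow-up tables, although the subject stays in earlier-period denominators.

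**Number of subjects.** 0.204 × 156 = 31.8, about 32 (0.204 × 104 = 21.2 dupilumab; 0.204 × 52 = 10.6 placebo). The share leaving with no follow-up visit is not given, so the range is 0 to about 32.

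**Treatment-emergent status.** Both documents run the treatment-emergent period from first dose to the end of the study. Protocol 6.1.4 defines that end at trial level, as the last subject's last visit. SAP 3.3 uses each subject's end-of-study visit, and SAP 5.7 detects events only up to EOS. A post-exit SAE is treatment-emergent on the first reading and not on the second.

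**Unnamed group.** The follow-up rule names early terminators from up-dosing and maintenance only. The membership rule in the same section speaks of entering follow-up from pre-dosing as well. Pre-dosing terminators who stay on study therefore have no defined follow-up dates.

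**The case against.** The strongest reply is that the design keeps these subjects. Protocol section 6.1 gives everyone a 12-week follow-up, including those who never reach 300 mg/day, and section 8.3.2 asks those who stop drug but remain on study to attend all remaining visits. SAP 3.3 defines a follow-up period for early treatment terminators, and SAP 6.4 (footnote e) lets an ET visit anchor visits 23 to 25. A reader might infer that every early terminator's off-drug SAEs are lost. The documents do not support that: those who attend follow-up are covered, as is any SAE with onset on or before the ET visit. This limits the point to subjects with no later visit.

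Second, protocol 10.4.2 concerns events the investigator happens to be told about; it is not scheduled follow-up, and section 10.4.6 ends AE collection at the last visit. A reader might multiply the protocol's figure of up to 20% not completing up-dosing by 156 subjects and 12 weeks (31.2 × 12 = 374 subject-weeks, about 7.2 subject-years) and call that lost follow-up. That assumes everyone leaves the study at an ET visit with *d* = 0 and treats unobserved time as observed. It should not be used.

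Third, a reader might conclude that the events vanish or survive only in listings. SAP 5.7.1 does list serious TEAEs and deaths, and protocol 11.4.4.1 promises SAEs and deaths summarized by treatment group, which SAP 1.2.3 does not withdraw. That stands, with one reservation: SAP 5.7 presents safety results by study period, so the SAP does not show how that summary would count a post-exit SAE.

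None of this answers the later-visit condition, which is an explicit rule.

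**Conclusion.** The gap is real and narrow. In subjects who leave with no follow-up visit, an SAE known to the investigator, with onset after the ET visit (or after last dose + 14 days) and within 12 weeks of last study drug, falls in no SAP 3.3 period. It is therefore absent from the per-period TEAE tables. Separately, the later-visit condition makes membership of the follow-up tables depend on surviving and being fit to return.

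The uncovered stretch is 70 of 84 days in the + 14 case and 84 − *d* days otherwise, with *d* unstated. The subject range of 0 to about 32 rests on borrowing the phase 3 discontinuation rate, and its upper end requires that nobody who discontinues has a follow-up visit. No expected number of SAEs can be derived. Few subjects may be involved, but the affected events are deaths and SAEs in a pediatric trial, and the correction is cheap before database lock.

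**What to change.** Amend SAP section 3.3:
1. For SAEs and deaths only, end the follow-up and overall study periods at the later of the subject's last visit and last study drug dose + 84 days. Other AEs keep the last visit as their limit, because collection stops there.
2. Drop the later-visit condition for AE, SAE and death tables. Include every treated subject who has left the treatment period, and name pre-dosing terminators. The condition can stay for by-visit laboratory and vital sign summaries.
3. Keep the treatment groups of SAP section 5, with dupilumab-then-placebo subjects shown separately. Assigning events to the last treatment received would fold them into placebo.
4. Reconcile the meaning of end of study across protocol 6.1.4, SAP 3.3 and SAP 5.7 so that these SAEs count as treatment-emergent.

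The cost is SAP wording and period-date programming, plus one reconciliation: protocol section 12.2 lists the pharmacovigilance safety database separately from EDC, and neither document says that post-exit SAEs reach the analysis data. The drawback is that SAEs after the last visit are passively ascertained. Mixing them with visit-based data can dilute incidence, so they should be footnoted in the tables.

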3.4. The Pharmacokinetic Analysis Set (PKAS)

The pharmacokinetic analysis set includes all treated subjects who received any study drug and who had at least one non-missing drug concentration result following the first dose of study drug.

3.5. The Immunogenicity Analysis Sets

The ADA analysis set (AAS) includes all treated subjects who received any study drug and who had at least one non-missing ADA result in the dupilumab ADA assay after first dose of the study drug. Subjects will be analyzed according to the treatment actually received.

The neutralizing antibody (NAb) Analysis Set (NAS) includes all treated subjects who received any study drug and who are negative in the dupilumab ADA assay or with at least 1 non-missing result in the dupilumab NAb assay. Subjects who are negative in the ADA assay are set to negative in the NAb analysis set. Subjects will be analyzed according to the treatment actually received.

3.6. Subgroups

Subgroups are defined by key baseline factors recorded on the eCRF (unless otherwise specified) and listed as the follows.

Subgroups to be considered for both efficacy and safety analyses:

- Age group (>=6 to <12 years, >=12 to <=17 years)
- Sex (Male, Female)
- Baseline weight group ($\leq 30 \text{ kg}, \geq 30 \leq 60 \text{ kg}, \geq 60 \text{ kg}$)
- Screening peanut-specific IgE level ($\leq 100 \text{ kUA/L or } > 100 \text{ kUA/L}$)
- Asthma and non-asthma history for primary and key secondary efficacy endpoint only
- AD and non-AD history for primary and key secondary efficacy endpoint only

4. ANALYSIS VARIABLES

4.1. Demographic and Baseline Characteristics

The following demographic and baseline characteristics variables will be summarized:

- Demographic variables
 - Age at screening (year)
 - Age group (≥ 6 to <12 years; ≥ 12 to ≤ 17 years)
 - Sex (Male, Female)
 - Race (White, Black or African American, Asian, American Indian or Alaska Native, Native Hawaiian or Pacific Islander, Other)
 - Ethnicity (Hispanic or Latino, Not Hispanic or Latino)
 - Baseline weight (kg)
 - Baseline weight category ($<30 \text{ kg}, \geq 30 \text{ kg}$ and $<60 \text{ kg}, \geq 60 \text{ kg}$)
 - Baseline height (m)
 - Baseline Body Mass Index (BMI) (kg/m²)
- Baseline characteristics
 - Duration of peanut allergy diagnosis (year)
 - Age at peanut allergy onset (year; <5, ≥ 5 and <10, ≥ 10 and ≤ 17)
 - Number of co-morbid atopic diseases (atopic dermatitis, asthma, nasal polyps, allergic rhinitis or eosinophilic esophagitis)
 - Baseline Fractional Exhaled Nitric Oxide (FeNO) value
 - History of atopic dermatitis (Yes, No)
 - Duration of atopic dermatitis disease with grouping (year; <=1 and >1)
 - Eczema Area and Severity Index (EASI) score for subjects with atopic dermatitis
 - History of asthma (Yes, No)
 - Asthma Control Questionnaire (ACQ-5) score for subjects with asthma
 - Baseline Food Allergy Quality of Life Questionnaire (FAQLQ) score for different types of FAQLQ form
 - Screening serum peanut-specific IgE
 - Screening serum peanut-specific IgG4
 - Screening serum total IgE
 - Screening peanut-specific IgG4/sIgE ratio

- Screening peanut-specific IgE level (≤100 kUA/L, >100 kUA/L)
- Baseline predicted FEV1 (L)
- Baseline percent predicted FEV1 (%)
- Baseline predicted FVC (L)
- Baseline percent predicted FVC (%)
- Maximum tolerated dose of peanut protein at screening DBPCFC
- Use of epinephrine at screening DBPCFC (Yes, No)
- Normalized mean peanut wheal diameter at screening SPT

Note: Normalized mean peanut wheal diameter is defined by mean peanut wheal minus mean saline wheal.

4.2. Medical History

Medical history will be coded to a Preferred Term (PT) and associated Primary System Organ Class (SOC) according to the latest available version of Medical Dictionary for Regulatory Activities (MedDRA[®]) by coding CRO.

Conditions related to subject's allergic and atopic medical history include peanut allergy, atopic dermatitis, asthma, allergic conjunctivitis, allergic rhinitis, chronic rhinosinusitis, nasal polyps, eosinophilic esophagitis, hives, contact dermatitis, egg allergy, milk allergy, tree nut allergy, fish allergy, shellfish allergy, wheat allergy, soy allergy, sesame or mustard seeds allergy, and other allergies (food, medications, animals, plants, mold, dust mite, etc.).

Conditions related to subject's family allergic and atopic medical history include atopic dermatitis, asthma, allergic conjunctivitis, allergic rhinitis, chronic rhinosinusitis, nasal polyps, eosinophilic esophagitis, food allergy, hives, contact dermatitis, other allergies (medications, animals, plants, mold, dust, mite, etc.).

4.3. Prior / Concomitant Medication and Procedures

Medications/Procedures will be recorded from the day of informed consent/assent until the endof-study (EOS) visit.

Medications will be coded to the ATC level 2 (therapeutic main group) and ATC level 4 (chemical/therapeutic subgroup), according to the latest available version of WHO Drug Dictionary (WHODD) at the coding CRO. Subjects will be counted once in all ATC categories linked to the medication.

Procedures will be coded to a Preferred Term (PT), High Level Term (HLT) and associated primary System Organ Class (SOC) according to the latest available version of MedDRA.

Prior medications/procedures: medications taken or procedures performed prior to administration of the first dose of dupilumab/placebo.

Concomitant medications/procedures (CMs/CPs): medications taken or procedures performed following the first dose of dupilumab/placebo through the EOS visit. This includes medications/procedures that were started before the study and are ongoing during the study. Furthermore, CM/CP will be categorized according to analysis periods (as defined in Section 3.3):

- CMs/CPs taken during the pre-dosing period
- CMs/CPs taken during the up-dosing period
- CMs/CPs taken during the maintenance period
- CMs/CPs taken during the follow-up period

4.4. **Prohibited or Rescue Medication/Procedure During Study**

Prohibited concomitant medications/procedures:

Treatment with the following concomitant medications is prohibited during the study:

- Treatment with a live (attenuated) vaccine (see protocol Section 8.7.1 for the list of vaccine)
- Treatment with any agents known or likely to interact with epinephrine (e.g., beta blockers, ACE-inhibitors, tri-cyclic antidepressants, or other drugs)
- Treatment with antihistamines within 5 days prior to screening and within 5 days prior to SPTs and day 1 of DBPCFCs

The following concomitant procedures are prohibited during study participation:

• Major elective surgical procedures

Rescue Treatment (including both medications and procedures)

The following concomitant treatments will require permanent study drug discontinuation:

- Treatment with an investigational drug (other than dupilumab)
- Treatment with immunomodulating biologic agents, including anti-IgE and anti-IL-5
- Treatment with allergen immunotherapy other than AR101
- Treatment with systemic (oral, IV, IM, SC) corticosteroids for a duration of more than 5 continuous days, more than 15 days in total, or within 2 days prior to DBPCFCs

The following concomitant treatments of allergic reactions will not require permanent study drug discontinuation.

- IM or SC administration of epinephrine
- Oral antihistamines
- Short acting inhaled bronchodilators
- Inhaled corticosteroids
- Systemic (oral, IV, IM, SC) corticosteroids for a duration of less than 5 continuous days, less than 15 days in total, and at least 2 days prior to DBPCFCs

CONFIDENTIAL

Page 23 of 86

Treatment of acute-allergic reactions will be categorized as follows,

- Screening DBPCFC of peanut protein
- Post up-dosing DBPCFC of peanut protein
- Post maintenance DBPCFC of peanut protein
- End of study DBPCFC of peanut protein
- Pre-dosing/up-dosing period (excluding post up-dosing DBPCFC)
- Maintenance period (excluding post maintenance DBPCFC)

Blinded adjudication of rescue treatments will be implemented before database locks by considering the type of medication or procedure, indication, timing, frequency and the potential impact of the use of the prohibited medication or procedure. The rescue treatments will be adjudicated by the clinical study director and the adjudication procedure will be documented.

